## **Duration of treatment**

26 weeks.

## **Measurements During follow-up:**

1. Clinical Outcomes:
  - a. Hospital readmissions, emergency department / urgent clinic visits for HF management and death (See appendix A: Heart Failure Hospitalization, ER visit and urgent outpatient clinic visit)
2. Glycemic control:
  - a. Mean daily fasting and pre-meal blood glucose levels.
  - b. HbA1c concentration at 12 and 26 weeks (T2D patients)
  - c. Number of hypoglycemic events
    - i. Clinically significant hypoglycemia defined as a BG < 54 mg/dl
    - ii. Symptomatic hypoglycemia defined as an event with typical symptoms (i.e., sweating, palpitation, and feeling of hunger) with or without confirmation by plasma glucose <70 mg/dl (3.9 mmol/L).
    - iii. Severe hypoglycemia defined as episodes necessitating assistance and associated with measured plasma glucose < 40 mg/dl (2.2 mmol/L) or with prompt recovery after administration of carbohydrates, glucagon, or other resuscitative actions. These episodes may be associated with sufficient neuroglycopenia to induce seizure or coma. Blood glucose measurements may not be available during such an event, but neurological recovery attributable to the restoration of BG to normal is considered sufficient evidence that the event was induced by low plasma glucose.
3. T2D treatment:
  - a. Number of patients receiving insulin therapy, dosage, and compliance.
  - b. Use of other oral agents, dosage, and compliance.
4. Blood pressure and heart rate
  - a. The most recent documented blood pressure (BP) of the day of screen can be used to determine enrollment eligibility. At randomization, the seated BP will be recorded in both the left and the right arms. Blood pressure (BP) and heart rate (HR) will be measured after the patient has been sitting and resting for at least 5 minutes. The arm with the highest seated systolic BP readings will be the one used for all subsequent readings (preferred arm).
5. Orthostatic blood pressure
  - a. Supine BP and pulse- The supine BP and pulse must be measured prior to the standing BP and pulse. After the patient rests in the supine position for at least 5 minutes, supine BP and pulse will be determined in the preferred arm

b. Standing BP and pulse - After the supine BP and pulse measurements are obtained, the patient will stand for 2 to 3 minutes. Standing BP and pulse will be determined from the preferred arm.

All readings must be recorded. For study analyses, the average of the BP and pulse readings will be used.

6. Anthropomorphic measurements

- a. Weight, height, waist, and hip circumference.
- b. Weight: Body weight will be measured without shoes and wearing light clothing.
- c. Height: Height (without shoes) will be measured in centimeters.
- d. Body Mass Index (BMI): BMI will be calculated by the formula: body weight (Kg)/m^2.

7. Six-minute walk distance (6MWD)

- a. The six-minute walk test requires a 100-ft hallway. This test measures the distance that a patient can quickly walk on a flat, hard surface in a period of 6 minutes. The six-minute walk test serves as a standardized test for functional capacity quantification of HF patients and is predictive of adverse cardiovascular outcomes . Most patients do not achieve maximal exercise capacity during the 6-minute walk test ; instead, they choose their own intensity of exercise and can stop and rest during the test.

9. Kansas City Cardiomyopathy Questionnaire (KCCQ) is a disease-specific health status instrument composed of 23 items that quantify the domains of physical limitation, symptoms, self-efficacy, social limitation, and quality of life limitation due to HF. Scores range from 0 to 100. For the KCCQ overall summary score, a small but clinically meaningful change is  $\geq 5$  points.

10. The Chronic Heart Failure Questionnaire (CHQ-SAS) is a validated questionnaire that assesses patients' perception of their HF and measures the impact of HF symptoms . The CHQ-SAS contains 16 standardized questions that assess dyspnea during daily activities, fatigue and emotional function. Items are rated on a 7-point Likert scale ranging from 1 to 7.

11. Echocardiogram

Echocardiograms will be performed at baseline (standard of care) and during follow-up. Echocardiographic measurements will include measurements of LV end-diastolic dimension (LVEDD), LV end-systolic dimension (LVESD), LV end-diastolic volume (LVEDV), LV end-systolic volume (LVESV), left atrial dimension (LAD), interventricular septal (IVS) and LV posterior wall (LVPW) thickness by 2D echocardiography or M-mode. LVEF assessment based on 2D echocardiography using the quantitative 2D biplane volumetric Simpson method from 4- and 2-chamber views. Patients with repeated echocardiography during the hospitalization or during follow-up, we will use the data from the examination performed closest to discharge.

12. Cost-effectiveness evaluation of resource utilization overall healthcare costs after hospital discharge in patients with ADHF. We propose to conduct an accompanying within-trial cost-effectiveness analysis using observed trial data. We will adopt a healthcare payer perspective for this analysis. The primary outcomes include total costs of trial participants. Per the recommendations of the Second Panel on Cost-Effectiveness in Health and Medicine and of the Consolidated Health Economic Reporting Standards (CHEERS), we will provide an impact inventory table and reporting checklist in our reports.

Data for cost outcomes will be derived from observed trial data based on abstraction of electronic medical record systems.

Costs: All costs will be expressed in uniform currency such as 2020 U.S. dollars. Total costs will include all direct costs associated with clinical care provided, and external health care service utilization (ER visits and hospitalizations). External healthcare service utilization will include routine office visits, after-hour clinic visits, after-hour clinic visits (urgent care), ambulance use, emergency room visits, and hospitalizations. To calculate the total costs of utilization at 6 months, the median prices of each healthcare service will be multiplied by the number of each service use during the trial.

13. Laboratory assessments. Blood and urine samples for determination of clinical chemistry, and NT proBNP levels will be obtained as per Study Plan. Serum magnesium and random urine sodium will be measured at baseline and repeated at 12 and 26 weeks.
14. Treatment Compliance/Adherence
  - e. The administration of study medication will be recorded. All stops of study medication prescribed by the investigator will be recorded. Study personnel will collect/record any decrease in oral agents and insulin dosage, and if the investigator determined to stop any previously used OADs or insulin during the study.
  - f. Missed doses of dapagliflozin or placebo blinded study medication will not be taken. If a dose is missed, the next regularly scheduled dose will be taken and will not be doubled.

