### Specific Aims:

**Aim 1: To determine whether the composite rate of hospital readmissions, emergency department, urgent clinic visits for HF and death are lower in patients with ADHF treated with dapagliflozin compared to those treated with placebo.** Patients with and without diabetes ADHF will be randomized to receive either dapagliflozin (10 mg once daily) or placebo at hospital discharge for 26 weeks.

**Hypothesis:** Treatment with dapagliflozin will significantly reduce the composite rate of hospital admissions, emergency department visits and urgent clinic visits for HF compared to placebo in patients discharged after an ADHF admission.

[figure not shown]
**Aim 2: To determine whether treatment with dapagliflozin compared to placebo will result in lower HF disease-specific biomarker (NT proBNP), improvement in glycemic control (HbA1c) in T2D patients, and improvement in symptoms and quality of life after hospital discharge in patients with ADHF.** We will measure changes in HbA1c, NT proBNP levels and HF-specific quality of life assessment using the Kansas City Cardiomyopathy Questionnaire (KCCQ) and improvement in symptoms using the Chronic Heart Failure Questionnaire (CHQ-SAS).

**Hypothesis:** Treatment with dapagliflozin will result in a greater improvement in HbA1c levels (in T2D patients), HF disease-specific marker (NT proBNP), quality of life (KCCQ scores), improvement of symptoms (CHQ-SAS scores) compared to placebo after hospital discharge at 12 and 26 weeks.

**Aim 3. Evaluate the within-trial cost-effectiveness of dapagliflozin compared to placebo in overall healthcare costs in patients with ADHF.** We will prospectively collect information on overall health care costs including emergency room visits, urgent clinic visits for HF, and hospitalizations between groups during the 6 months of intervention.

**Hypothesis:** Treatment with dapagliflozin will be associated lower resource utilization and health care costs compared to placebo after hospital discharge.

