**Cost-Effectiveness Analyses:** The endpoints include healthcare charges, and numbers and incidences of emergency room visits, urgent clinic visits for HF, and hospitalizations. For continuous outcomes (e.g. charges), we will use Wilcoxon rank-sum test to compare them between the two groups. Linear regression or quantile regression will be performed to assess the group difference adjusting for other potential confounders such as baseline utility scores. The Chi-square test will be used to compare categorical outcomes (e.g. categorized frequency of emergence room visits), followed by generalized linear models (e.g. logistic regression model) which adjusts for other potential confounders. To model repeatedly measured cost-related outcomes (e.g. utility scores) over time, repeated measures analyses via linear mixed models or generalized linear mixed model will also be performed to estimate the effect of dapagliflozin, time, and their interaction. Potential covariates such as age, gender, race, insurance, and duration of T2D, along with baseline utility score, will be adjusted. Standard model selection and checking procedures will be applied to ensure the adequacy of the adopted models.

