**Confidentiality.** Informed consent will follow the procedure of Emory University Institutional Review Board. Every potential participant will be informed in writing and verbally with the important and key points of the study. The research team will obtain a witnessed informed consent prior to inclusion of a patient into the study. Data collection records with personal identifiers will be stored in locked file cabinets. Presentation of the study results at scientific meetings or in publications will not identify subjects. Access to research and confidential records will be limited to clinical investigators, coordinators and the IRB at Emory University.

**Payment for Participation.** Participation in this study is voluntary. Patients will receive twenty-five dollars (\$25.00) during the hospital stay and visit 2, and fifty dollars (\$50.00) after each clinic visit after discharge. Total compensation up to three hundred dollars (\$300).

**Financial Obligation.** No additional cost to patients or to the institution will be incurred for research purposes. Research studies will be performed at no cost to study subjects. Dapagliflozin and matching placebo will be provided by the sponsor at no cost to participants.

**Research Injuries.** If a patient is injured because of taking part in this study, [name] and investigators, along with the medical facility will make medical care available to the patient at the patient's own cost. Financial compensation for such things as lost wages, disability or discomfort due to an injury related to the study is not available.

**Financial Conflict of Interests.** None of the investigators in this study have any outside activities that may represent a conflict of interest. None of the investigators have an economic interest in an outside entity, or act as officers, directors, employees or consultants with such an entity, whose financial interest may be affected by this research study.

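### Aim 3 compares payer costs, but the plan gives no price, quantity or data source for dapagliflozin, so as written the active arm would be charged nothing for the drug

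*Combined protocol and SAP*

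**What the plan says.** Aim 3 under Specific Aims reads: "Evaluate the within-trial cost-effectiveness of dapagliflozin compared to placebo in overall healthcare costs in patients with ADHF". Its hypothesis is directional: "Treatment with dapagliflozin will be associated lower resource utilization and health care costs compared to placebo after hospital discharge".

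Item 12 of Measurements During follow-up sets the viewpoint: "We will adopt a healthcare payer perspective for this analysis". It names total costs of participants as a primary outcome of this analysis and takes cost data from abstraction of electronic medical records. On content it says: "Total costs will include all direct costs associated with clinical care provided, and external health care service utilization (ER visits and hospitalizations". It then lists the services: "External healthcare service utilization will include routine office visits, after-hour clinic visits", followed by urgent care, ambulance use, emergency room visits and hospitalizations. To value utilization at 6 months, a median price per service "will be multiplied by the number of each service use during the trial".

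The Cost-Effectiveness Analyses paragraph of the Statistical Methods says: "The endpoints include healthcare charges, and numbers and incidences of emergency room visits, urgent clinic visits for HF, and hospitalizations".

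The Financial Obligation paragraph says: "Dapagliflozin and matching placebo will be provided by the sponsor at no cost to participants".

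**The concern.** A payer that adopts dapagliflozin has to buy it. A payer-perspective total that counts any admissions and visits the drug avoids, but not the drug itself, answers a narrower question than Aim 3 asks. The documents give no unit price for dapagliflozin, no price source, no rule for counting tablets for costing, and no statement that the drug is in or out of the total. Because it is supplied free, a payer charge for it would not be expected in the abstracted records.

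If the term is missing, the error has one direction. It lowers the active arm's total, leaves placebo unchanged, and so leans towards the stated hypothesis. A reported cost saving could not then be read as a saving to a payer outside the trial.

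**Working it through.** The plan states no cost figure, so there is no number to reproduce. The check has two parts: whether any step would bring in the drug, and how large the missing term is.

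**Does any step price the drug?**

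| Element of the plan | Content | Brings in study drug? |
|---|---|---|
| Cost components (item 12) | Direct costs of clinical care, plus external service use | Possibly, for the first component, but no quantity, price or source is attached |
| Listed services (item 12) | Office, after-hours and urgent visits, ambulance, ER, hospitalization | No |
| Valuation rule (item 12) | Median service price times number of uses, for utilization costs | No |
| Data source (item 12) | Medical-record abstraction | Not expected, since supply is free |
| Endpoints (Cost-Effectiveness Analyses) | Charges, ER and urgent visits, hospitalizations | Not named |
| Drug Accountability (item 15) | Tablets dispensed and returned | Holds the quantity, but is not linked to cost |

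No row supplies both a quantity and a price for dapagliflozin.

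**Size of the missing term**

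Inputs from the documents:
- One 10 mg dose daily, 196 patients in the active arm (Investigational Drugs).
- 26 weeks of treatment (Duration of treatment).
- Three bottles of 35 tablets at each of two dispensings (Drug Dispensing Scheme).
- Placebo event rate 40% to 60%, with 50% used for sample size, and a 30% relative reduction (Sample Size and Power Calculations).

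Let X be the payer price per tablet. The documents do not give it.

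- Doses per fully adherent patient: 26 × 7 = 182.
- Tablets dispensed per patient: 2 × 3 × 35 = 210.
- Missing cost per active patient: 182X if doses taken are charged with full adherence, 210X if all dispensed tablets are charged. Placebo: 0.
- Whole active arm at full adherence: 196 × 182X = 35,672X.

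Illustration with X assumed at $5 to $20:
- Per patient, 182 doses: 182 × 5 = $910 to 182 × 20 = $3,640.
- Per patient, 210 tablets: 210 × 5 = $1,050 to 210 × 20 = $4,200.
- 196 patients at 182 doses: $178,360 to $713,440.

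**What an averted event would have to save**

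Under the plan's 50% versus 35% rates, 0.50 × 0.30 = 0.15 first-event patients are averted per patient treated. With the drug charged, the active arm is cheaper only if the mean saving per averted first-event patient exceeds 182X / 0.15, about 1,213X. The multiplier at the ends of the plan's range is:
- placebo rate 40%: 182X / 0.12, about 1,517X;
- placebo rate 60%: 182X / 0.18, about 1,011X.

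At 50% and X of $5 to $20, the threshold is about $6,067 to $24,267. This is illustrative only. It counts one event per affected patient although the plan multiplies by every service used, treats hospitalizations, ER visits, clinic visits and deaths alike, covers only the HF composite, and assumes full adherence. These simplifications do not all push the same way.

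**The case against.** The strongest reply is that the plan does not exclude the drug. Item 12 gives total cost two components. The multiplication rule is introduced as a way to value utilization, so on its wording it governs only the second. The first, direct costs of clinical care, has no valuation rule and could take in dapagliflozin. This stands: a reader might infer that the plan deliberately leaves drug cost out, and the text does not say that. The gap is one of silence. It still matters, because the stated data source, the listed services and the listed endpoints give an analyst nothing to enter for the drug.

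Item 12 also promises an impact inventory table and a reporting checklist, where included and excluded costs might be shown. That tempers any claim of exclusion, but the protocol does not say which lines will appear, and a reporting table does not provide a price or a calculation.

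Other drug costs are equally unnamed: insulin and oral agents are recorded during follow-up but do not appear in the cost list. That is fair, and a clear cost boundary should say whether they count. They differ from the study drug in that both arms may use them, whereas dapagliflozin as study treatment falls on one arm only.

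Finally, cost is not among the listed primary or secondary endpoints, and tablet counts are already collected, so the term can be added at analysis without loss of data. That limits the consequence and makes the repair easy. It does not remove the need to fix the price before results are known.

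**Conclusion.** The point holds in this form: the plan does not state whether or how study-drug cost enters total cost, and the steps it does give would record $0 for dapagliflozin. Any resulting bias favours the active arm. Its size is 182X per fully adherent active patient, or 210X if all dispensed tablets are charged, against zero on placebo.

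A reader might go further and infer that the sign of the cost difference will be wrong. The documents do not support that. They contain neither a drug price nor a unit cost for any event, so a break-even value reflects whatever ranges are assumed. What can be said is that the sign depends on a quantity that the plan does not specify.

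The point is confined to Aim 3 and leaves the primary endpoint and sample size untouched. It should be settled before the cost analysis is run.

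**What to change.** In item 12 of Measurements During follow-up and in the Cost-Effectiveness Analyses paragraph:

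1. State that total cost in the active arm includes dapagliflozin acquisition cost, and that this term is zero for placebo.
2. Define it as tablets from the drug-accountability records times a prespecified payer price. Say whether tablets are those dispensed or those taken (dispensed minus returned), name the price source, and give a range for sensitivity analysis.
3. Report the service-only total separately, labelled as utilization cost excluding study drug.
4. In the same text, say whether background glucose-lowering drugs are inside the cost boundary.

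The cost is a few sentences of protocol or SAP wording and a little more analysis, using tablet counts already collected. No new visits or patients are needed. The downside is a cost result less favourable to dapagliflozin than a service-only total.

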### **Patient refuses any form of follow-up**

If the patient refuses any form of follow-up, he/she officially withdraws from the study and withdraws consent. This decision must be documented. At the end of the study, vital status on all such patients will be collected from publicly available sources, in accordance with local regulations.

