SGLT2-is have been shown to markedly reduced HF hospital admissions in patients with and without diabetes. In the CVD-Real Study, which included 961 HF cases, SGLT2-i reduced the rates of HF hospitalizations hazard ratio, 0.61; 95% confidence interval, 0.51-0.73; P<0.001. The CVD-Real 2 multinational study of 235,064 patients with T2D, initiation of an SGLT-2i was also associated with a lower risk of all-cause death and hospitalization for heart failure, as compared to other glucose lowering drugs. The use of SGLT-2i vs. other glucose lowering drugs was associated with lower risk of death and heart failure. Recent RCT examining cardiovascular outcome using SGLT2-i reported a significant reduction in hospitalization for HF. In the DECLARE trial, dapagliflozin resulted in lower rate of hospitalization for heart failure compared to placebo (HR, 0.73; 95% CI, 0.61 to 0.88). The EMPA-REG OUTCOME study showed a 35% reduction in HF hospitalizations. In addition, in the CANVAS Program the benefits were greater in patients with a previous history of HF compared with those without HF at baseline (HR, 0.87; 95% CI, 0.72–1.06; P interaction = 0.021). In the Canvas Program, the rate of HF was reduced in patients with history of HF from 28.1% to 14.1% between patients treated with canagliflozin and placebo.

Based on data summarized above, we assume the composite event rate in the placebo group is between 40-60%, which would be reduced by 30% in the dapagliflozin group. Based on two-sided Chi-square test, with preserved alpha=0.05, with 176 subjects, we would achieve over 80% power to detect a 30% reduction in proportion of patients with readmission, ER visits, urgent unplanned clinic visit for HF or death if the composite event rate in the placebo group is 50%. Accounting for 10% attrition, we propose to recruit 392 patients (196 per group).

In the table below, we provide estimated power based on the same method, corresponding to different placebo composite event rates that are between 40-60%:

Composite event rate in the placebo group	40%	45%	50%	55%	60%
Estimated Power	62%	72%	82%	88%	93%

The results in the above table suggest promising power for the proposed study.

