#### **Analysis of Primary Endpoint:**

We will first compare the proportion of patients with at least 1 readmission, ER visit or unplanned urgent clinic visit for HF or death between the two study groups, using Chi-squares test or Fisher’s Exact tests. Logistic regression will be conducted to adjust for the effects of other potential confounders (e.g. age, gender). Stepwise, backward, or forward model selection strategy will be adopted to determine the variables to be included in the final model. Standard diagnostic and model checking procedures,

such as deviance residual plot and Hosmer- Lemeshow test, will be applied to examine the fit of the developed models.

**Analysis of Secondary Endpoints:** The secondary endpoints include continuous longitudinal outcomes (e.g. change in KCCQ score from baseline at 6, 12, and 26 weeks), and discrete outcomes (e.g. whether patients with a  $\geq 5$ pts increase in KCCQ score). To analyze continuous longitudinal outcomes, we will first conduct cross-sectional analyses based on nonparametric Wilcoxon tests (or t-tests), followed by multivariate linear regression, where responses may be transformed to better meet the normality assumption. Then we will apply repeated measures ANOVA or repeated measures linear regression model to assess the outcome differences between the two study groups, simultaneously evaluating the outcomes measured at different time points while appropriately accommodating the within-subject correlations. For discrete outcomes, we will conduct univariate analyses based on Chi-square tests (or Fisher's Exact tests). For binary discrete outcomes, we will use logistic regression models to account for the effects of other potential confounders. For other types of discrete outcome (e.g. counts), we will apply Poisson regression models or Negative Binomial regression models to address the confounding effects of other variables. Standard model selection and checking procedures will be applied to ensure the adequacy of the adopted models.

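### The six-month cost total has no rule for patients whose service use is only partly observed, so partial totals can enter the comparison as 26-week totals

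*Combined protocol and SAP*

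**What the plan says.** Aim 3 asks whether dapagliflozin lowers resource use and health care cost over the six months of intervention. Item 12 of Measurements During follow-up gives the outcome and the rule:

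- Outcome: "The primary outcomes include total costs of trial participants".
- Horizon: "To calculate the total costs of utilization at 6 months", the median price of each service "will be multiplied by the number of each service use during the trial".
- Source: "Data for cost outcomes will be derived from observed trial data based on abstraction of electronic medical record systems".

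The analysis is in Cost-Effectiveness Analyses under Statistical Methods: "For continuous outcomes (e.g. charges), we will use Wilcoxon rank-sum test to compare them between the two groups". Linear or quantile regression follows for the adjusted comparison. Neither place defines a cost analysis set, a date to which records are searched, or a method for patients observed for less than 26 weeks.

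Three other sections decide who is only partly observed. Patients who stop study drug are asked to keep attending visits. Patients who refuse visits but accept modified follow-up are contacted to find endpoints and safety events, and have not withdrawn consent. Patients who refuse all follow-up withdraw consent, and for them "At the end of the study, vital status on all such patients will be collected from publicly available sources". The section on patients lost to follow-up promises repeated attempts to locate them and obtain medical information, but sets no rule for their cost.

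**The concern.** A total built from six weeks of observation is not a low 26-week cost. It is a 26-week cost of which only the first part was seen. Item 12 makes no distinction: the number of uses recorded becomes the six-month total for every participant. Death is different, because use and cost after death are truly zero, so a patient who died under observation has a complete cost.

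Two things are at stake. Absolute mean costs, which a payer-perspective analysis reports, come out too low in both arms. If the arms lose different numbers of patients, or lose them at different times, the totals can also differ with no effect of treatment on use. Because the plan sets no rule, the analyst would have to choose one after the data are in.

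**Working it through.** **Inputs.** The plan gives no unit price, cost standard deviation, withdrawal rate by arm or withdrawal timing, so no corrected cost can be computed. The only relevant figure is the 10% attrition in Sample Size and Power Calculations.

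**The plan's own figure.** 176 / (1 − 0.10) = 195.6, which rounds up to 196 per group and 392 in all, as stated. With 176 per group and 50% versus 35%, a two-sided chi-square test has 81.5% power, against the stated 82%. The 10% is therefore an allowance for the primary endpoint: 0.10 × 392 = 39.2 patients, or 19.6 per arm. It is not a forecast of missing cost data, and serves here as an upper illustration.

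**Formula.** Let d be the share of an arm that is cost-censored and f the mean share of the 26-week cost already recorded at exit. Then

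recorded mean / true mean = 1 − d(1 − f).

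Uniform exit times and a constant use rate give f = 0.50. Earlier exit lowers f. Later exit, or use concentrated soon after discharge, raises it. The range 0.25 to 0.75 is an assumption.

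**Equal loss, 10% in each arm.** At f = 0.50: 1 − 0.10 × 0.50 = 0.95, so each mean is 5.0% too low. At f = 0.25 and 0.75 the shortfall is 7.5% and 2.5%. The ratio between arms stays at 1.00.

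**Unequal loss, no true difference.** The entries show how much cheaper the arm losing more appears. The splits are assumptions; each averages 10%.

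| Loss | f = 0.25 | f = 0.50 | f = 0.75 |
|---|---|---|---|
| 8% vs 12% | 3.2% | 2.1% | 1.0% |
| 5% vs 15% | 7.8% | 5.1% | 2.5% |

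For 5% versus 15% at f = 0.50: (1 − 0.15 × 0.50) / (1 − 0.05 × 0.50) = 0.925 / 0.975 = 0.949.

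**Unequal timing.** With 10% lost in both arms but f = 0.75 in one and 0.25 in the other: 0.925 / 0.975 = 0.949, again about 5%.

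**The planned test.** I simulated 196 patients per arm with no true difference, uniform exit times and 3,000 runs. Assumed use was one overdispersed admission per 26 weeks at 10,000 and five visits at 200. The Wilcoxon test at nominal 5% rejected in 4.9% of runs with no loss, 4.8% with 10% loss in both arms, and 12.6% with 5% versus 15%. The last figure depends on the assumed split and prices. It shows only that a rank test on unadjusted totals is not protected against unequal loss.

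**The case against.** The strongest reply is that ascertainment of cost does not depend on attending visits. Medical record abstraction can continue after contact stops. Stopping study drug is not leaving the trial, and modified follow-up still looks for endpoints and safety events. Those include heart failure admissions, emergency and urgent visits, and other admissions that qualify as serious adverse events, which are likely to be the main cost items. Most of this stands. Clear censoring is confined to patients who refuse all contact and those never located. What remains is that the plan does not promise record review to week 26, does not say how care at other institutions is captured, and does not mention routine office visits or ambulance use in modified follow-up, although item 12 lists both as services to be counted.

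Mixed models are planned for repeatedly measured cost-related outcomes and could use partial follow-up. Their stated example is utility scores, however, not the six-month total.

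A reader might infer three stronger points, which the documents do not support:

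- *That the plan counts early leavers as complete.* It nowhere says so. This is the literal consequence of item 12, in the absence of any other rule.
- *That drug-related withdrawal will make dapagliflozin look cheaper.* The Safety section quotes genital infections that were serious or led to discontinuation at 0.9% versus 0.1%, and calls discontinuation rare. If the whole 0.8-point gap became full withdrawal, the bias at f = 0.50 would be 0.008 × 0.50 = 0.4%. Patients on placebo might equally leave for lack of benefit.
- *That the planned count models are wrong because they name no offset.* The sentence "we will apply Poisson regression models or Negative Binomial regression models" belongs to the secondary endpoints, and no visit count is listed among those. Admission and visit counts fall under Cost-Effectiveness Analyses, which names other methods.

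**Conclusion.** The point holds as a gap in the cost rule and its analysis. It affects Aim 3 only and leaves the primary endpoint untouched. Applied as written, item 12 treats partial totals as 26-week totals for patients who withdraw consent or are lost. The understatement of each arm's mean is up to about 5% if all 10% attrition is cost-censored with uniform exit and constant use, and less to the extent that records fill the gap. It could exceed 5% if patients leave early or if those who leave use more care.

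A bias between arms needs unequal loss or unequal timing. It is about 5% at an assumed 5% versus 15% and about 2% at 8% versus 12%. The documents give no basis for any particular split, so neither its size nor its direction can be predicted. That uncertainty is the reason to fix the rule in advance.

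**What to change.** Amend item 12 of Measurements During follow-up and the Cost-Effectiveness Analyses paragraph as follows.

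1. Abstract records to day 182 (26 × 7) for every participant whose consent allows it. Record for each the date of last complete utilization capture. Visit dates do not supply this, because they do not show when record coverage ended.
2. Define the cost analysis set as all randomized patients. Treat withdrawal of consent and loss to follow-up as censoring at the recorded date. Treat death as complete, with zero further use and cost.
3. Make a censored-cost estimate of each arm's mean 26-week cost the main cost comparison, for example by inverse-probability-of-censoring weighting. Multiple imputation is a reasonable alternative. With at most about 20 censored patients per arm, keep the censoring model small. Both methods assume that exit is non-informative given the variables modelled. Keep the Wilcoxon test on unadjusted totals as supportive.
4. For admission and visit counts, use negative binomial regression with a log offset for days of ascertainment, shortened only by withdrawal or loss. Patients who die keep the full 182 days. Ending the offset at death would estimate a rate while alive, which is not the 26-week total.

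The cost is one extra date per patient, record review to day 182, modest programming and slightly wider intervals. No extra visits or patients are needed.
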